**Table 5.1: Patritumab Maintenance Dose Modification for Toxicities**

Toxicity	Withhold Criteria	Resumption Criteria	Dose Reduction Criteria	Discontinuation Criteria
All AEs a	Grade 3 or higher	Grade 0 or 1 (or baseline grade if higher than Grade 1) b	Reduce patritumab maintenance dose from 9 mg/kg to 6 mg/kg (for mucositis follow dose modification as defined above)	Failure to recover within 3 weeks

Toxicity	Withhold Criteria	Resumption Criteria	Dose Reduction Criteria	Discontinuation Criteria
Ejection fraction	Grade greater than or equal to 3, (LVEF of less than 40% or LVEF decrease of more than 20% from the baseline)	LVEF of at least 50% (or baseline) based on a repeat echocardiogram or MUGA scan performed in 3 weeks	Reduce patritumab maintenance dose from 9 mg/kg to 6 mg/kg	LVEF that does not recover within 3 weeks: Decreased $\geq$ Grade 3 <40% >20% decrease from baseline

a For elevations of aminotransferase (AST/ALT) and/or bilirubin, please see Section 4.1.4.

b Patritumab/placebo dosing may be resumed upon consultation with the Sponsor's medical monitor if the event has resolved to Grade 2.

MUGA = multigated acquisition (scan); LVEF = left ventricular ejection fraction.

Dose delays/reductions for toxicities related to patritumab are summarized in Table 5.2.

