#### 4.1.2. Exclusion Criteria

Subjects who meet any of the following criteria will be disqualified from entering the study:

1. Left ventricular ejection fraction (LVEF) <50%
2. Prior EGFR targeted regimen
3. No HRG expression result
4. No HPV or p16 status
5. Prior anti-HER3 therapy
6. Prior chemotherapy for recurrent/metastatic disease
7. Anti-cancer therapy between biopsy and submission of sample
8. Presence of squamous cell tumors of the nasopharynx
9. History of other malignancies, except adequately treated non-melanoma skin cancer, curatively treated in-situ disease, or other solid tumors curatively treated with no evidence of disease for  $\geq 2$  years
10. Known history of brain metastases or active brain metastases
11. Uncontrolled hypertension (systolic > 160 mm Hg or diastolic > 100 mm Hg)
12. Clinically significant electrocardiograph (ECG) findings
13. Myocardial infarction within 1 year before enrollment, symptomatic congestive heart failure (New York Heart Association >Class II), unstable angina, or unstable cardiac arrhythmia requiring medication
14. Platinum-containing drug therapy with radiotherapy less than 6 months before study drug treatment
15. Therapeutic or palliative radiation therapy or major surgery within 4 weeks before study drug treatment. Radiation treatment to all sites of measureable disease unless progression is documented after radiation
16. Participated in clinical drug trials within 4 weeks before study drug treatment. Current participation in other investigational procedures
17. Uncontrolled infection requiring IV antibiotics, antivirals, or antifungals, known HIV infection, or active hepatitis B or C infection or undergoing medical treatment for infection
18. Uncontrolled type 1 or 2 diabetes mellitus
19. Known hypersensitivity or allergic reaction against any of the components of the trial treatment
20. Pregnant, breastfeeding, or unwilling/unable to use acceptable contraception
21. Residual toxicities  $\geq$  Grade 1 from previous therapies that the Investigator determines would exclude participation

22. Psychological, social, familial, or geographical factors that would interfere with study participation or follow-up
23. Committed to an institution by virtue of an order issued either by judicial or administrative authorities
24. Employee or immediate relative of an employee of the sponsor, CRO, the study center, or their affiliates or partners

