### 5.1.7.1. Dose Modification of Patritumab

Patritumab is contraindicated for subjects with known hypersensitivity to either the drug substance or inactive ingredients in the drug product. In previous patritumab studies, the most common toxicities that occurred were rash, diarrhea, vomiting, nausea, fatigue, dyspnea, and skin and subcutaneous tissue disorders. Table 5.1 and Table 5.2 pertain to patritumab dose modifications.

If the initial loading dose of 18 mg/kg is not tolerated, infusion time can be extended to a maximum of 120 minutes for subjects unable to tolerate the 60 minute infusion. Patritumab/placebo is to be withheld from a subject experiencing a CTCAE Grade 3 AE, and resumed at the next regularly scheduled patritumab dosing (maintenance dose of 9 mg/kg) only after resolution of the AE to Grade 0 or 1 (or baseline grade if higher than Grade 1).

If a rash or mucositis occurs following the initial dose of patritumab 18 mg/kg, then hold the patritumab until the AE resolves to Grade 0 or 1 (or baseline grade if higher than Grade 1). If the rash or mucositis has not resolved, then hold cetuximab 250 mg/m^2 until the AE resolves to Grade 0 or 1 (or baseline grade if higher than Grade 1). If a rash or mucositis occurs on the maintenance dose of patritumab at 9 mg/kg, hold patritumab until the AE resolves to Grade 0 or 1 (or baseline grade if higher than Grade 1) and then decrease patritumab dosing to 6 mg/kg. If the AE does not resolve, hold the next dose of cetuximab until resolution to Grade 0 or 1 (or baseline grade if higher than Grade 1).

Left ventricular ejection fraction will be monitored throughout the study (see Section 9.11.1) for possible effects of patritumab treatment on cardiac function. Dose modification or suspension of patritumab treatment will be based on decreased LVEF, as outlined in Table 5.1.

For cases of ILD, refer to Section 9.3.2.

Both patritumab/placebo are to be withheld from a subject experiencing a Grade 4 AE.

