**Table 5.2: Dose Delays/Reductions for Toxicities Related to Patritumab**

Grade	Action
1	Continue current dose level
2	Continue current dose level
3	Discontinue patritumab/placebo for up to 3 weeks until the event has recovered to Grade 1 or baseline. a Administer patritumab at a dose that is decreased by one dose level for subsequent cycles. A maximum of 1 dose reduction from the 9 mg/kg IV maintenance dose to 6 mg/kg IV maintenance dose will be permitted. No dose reductions below patritumab 6 mg/kg will be allowed.
4	Discontinue patritumab/placebo for up to 3 weeks until the event recovers to Grade 1 or baseline. a Discuss the event with the sponsor's Medical Monitor or designee before restarting patritumab/placebo. If the investigator and the sponsor's Medical Monitor/designee agree, the weekly maintenance dose will also be decreased from 9 mg/kg IV to 6 mg/kg IV.

a If the subject fails to recover to Grade 1 or baseline and dose must be delayed >3 weeks, the subject will be withdrawn from all study treatment, but should continue to undergo all follow-up evaluations

To receive patritumab, a subject's ANC must be  $\geq 1.5 \times 10^9/L$  ( $\geq 1500/mm^3$ ) and platelet count must be  $\geq 100 \times 10^9/L$  ( $\geq 100,000/mm^3$ ). Patritumab may be withheld for up to 3 weeks to allow cell counts to recover to these values. Dose administration may be delayed no more than 3 weeks to allow for recovery. If the dose is delayed more than 3 weeks, the subject will be withdrawn from study treatment, unless discussed and agreed with the sponsor.

All subjects should be carefully monitored for possible infusion reactions during the administration of patritumab/placebo. If, during infusion, a subject experiences mild to moderate symptoms suggestive of infusion reaction (such as fever and chills, with or without nausea/vomiting, pain, headache, dizziness, dyspnea, hypotension), slow down the infusion up to 120 minutes (see Section 3.1.2.1 for administration of patritumab/placebo). All subsequent infusions should be administered at the same slow rate (up to 120 minutes).

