## **9.11. Other Safety Assessments**

### **9.11.1. Echocardiograms or MUGA (LVEF Assessment)**

To monitor for possible effects of treatment on cardiac function, LVEF will be assessed at Screening, Cycle 3, and then every third subsequent cycle, the End of Treatment Visit, and as otherwise clinically indicated using either echocardiography or MUGA scanning (if MUGA is considered local standard of care). The same test must be used for a subject throughout the study. Clinically significant changes from baseline in LVEF will be reported as AEs.

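### In Table 5.1, at high baseline LVEF, a 3-week scan can meet the resumption cell while still meeting the same row's withhold criterion, and no text says which rule governs

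*Protocol*

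**What the plan says.** Protocol Section 5.1.7.1 sends cardiac dosing decisions to one table: "Dose modification or suspension of patritumab treatment will be based on decreased LVEF, as outlined in Table 5.1". The LVEF row of Table 5.1 then has four parts.

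- **Withhold:** Grade 3 or higher, explained in brackets as "LVEF of less than 40% or LVEF decrease of more than 20% from the baseline".
- **Resume:** "LVEF of at least 50% (or baseline) based on a repeat echocardiogram or MUGA scan performed in 3 weeks".
- **Dose on resumption:** 6 mg/kg instead of 9 mg/kg.
- **Discontinue:** no recovery within 3 weeks, followed by a list that includes ">20% decrease from baseline".

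The general toxicity rules sit alongside this row. Section 5.1.7.1 lets patritumab/placebo resume after a Grade 3 event "only after resolution of the AE to Grade 0 or 1" (or the baseline grade if that was higher). The All AEs row of Table 5.1 has the same resumption grade. Table 5.2 says for Grade 3: "Discontinue patritumab/placebo for up to 3 weeks until the event has recovered to Grade 1 or baseline".

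Two other provisions matter. Exclusion criterion 1 in Section 4.1.2 is "Left ventricular ejection fraction (LVEF) <50" (percent), so every eligible baseline is 50% or more. Section 9.11.1 sets the monitoring schedule: "LVEF will be assessed at Screening, Cycle 3, and then every third subsequent cycle", plus the end-of-treatment visit and whenever clinically indicated.

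**The concern.** The withhold cell looks at both the absolute level and the change from baseline. The resumption cell looks only at the level, apart from its bracketed reference to baseline. A subject who starts high can therefore clear the 50% floor while the drop that caused the hold is still present. The row does not say which cell then decides.

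Two sites with the same scan could act differently. One restarts at 6 mg/kg. The other keeps withholding, or stops, and under Section 5.1.7 a subject who has to discontinue patritumab/placebo is withdrawn from the study. The first site may re-expose a subject whose LVEF is still well below baseline, and the next scheduled scan may be some weeks away. LVEF is followed specifically to detect cardiac effects of patritumab, so the stop and restart rule should give one answer.

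**Working it through.** The plan states no figure to reproduce. The check is an overlap of the thresholds in the LVEF row.

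**Inputs.** Baseline b is at least 50 (Section 4.1.2). The resumption floor is x of at least 50 on the 3-week scan, and the withhold criterion is x below 40 or a drop of more than 20% (both Table 5.1). The row does not say whether 20% is in percentage points or relative, so both meanings are carried.

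**Where overlap begins.** The lowest reading that allows resumption is 50.

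- Points: b − 50 > 20, so b > 70.
- Relative: 50 < 0.8 × b, so b > 50 / 0.8 = 62.5.

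**Which readings overlap.** These are whole-percent 3-week readings x of at least 50 with b − x > 20 (points) or x < 0.8b (relative):

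| Baseline | 20% as points | 20% as relative |
|---|---|---|
| 65% | none | 50–51% |
| 70% | none | 50–55% |
| 72% | 50–51% | 50–57% |
| 75% | 50–54% | 50–59% |
| 80% | 50–59% | 50–63% |

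**Worked case.** Baseline is 72%, an on-study scan reads 51%, the drug is held, and the 3-week repeat is again 51%. The drop is 72 − 51 = 21 points, or 21 / 72 = 29.2%. The repeat meets the resumption cell. It also meets the withhold cell under either meaning of 20%, and so is still Grade 3 or higher on the row's own terms. It matches the drop listed in the discontinuation cell too, but whether that cell applies depends on what recovery means, and recovery is not defined.

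**Does the bracketed reference to baseline resolve it?** It is worded as an alternative to 50%. Since no eligible baseline is below 50%, it cannot lower the floor, and as an alternative it cannot raise it. If a full return to baseline was intended, the conflict would disappear, but the cell does not say so.

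**Time to the next scheduled scan.** Scans fall on Day 1 of Cycles 3, 6, 9 and so on (Sections 6.2.6.2 and 6.2.7.1). Suppose the hold follows the Cycle 3 scan and the repeat is 3 weeks later. If cycle numbers run on, Cycle 6 Day 1 is 2 × 21 = 42 days (6 weeks) after the repeat, with doses at Cycles 4 and 5 first. If the withheld cycle is not counted, it is 3 × 21 = 63 days (9 weeks), with three doses first. The documents do not say which numbering applies.

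**With the overlap closed.** Adding the drop limit makes the resumption floor the larger of 50 and b − 20 (points), or the larger of 50 and 0.8b (relative). At b = 75 that is 55% or 60%; at b = 65 it is 50% or 52%. No reading then meets both cells under the same meaning of 20%.

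**The case against.** The best counter-argument is that the protocol already answers the question. Section 9.11.1 makes clinically significant LVEF changes reportable as adverse events. Following Section 5.1.7.1 into Table 5.1 therefore also leads to the All AEs row, which requires Grade 0 or 1 (or the baseline grade) before resumption. The only exemption marked on that row is for aminotransferases and bilirubin. The LVEF row itself grades a drop of more than 20% as 3 or above, so the worked case would not qualify. Table 5.2 agrees. Meeting a resumption criterion does not oblige anyone to dose while a withhold criterion stands, and Section 5.1.7 lets the investigator withhold until Grade 0 or 1. Section 5.1.7.1 also says the medical monitor should be consulted when a specific dose modification is needed, and a restart at 6 mg/kg is one.

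Most of this stands, and it makes the practical risk small. A reader might infer that the protocol directs sites to re-treat subjects with a persistent Grade 3 drop, or leaves the decision wholly open. The documents support neither: several provisions point away from restarting. What remains is narrower. The LVEF row has its own resumption cell, Section 5.1.7.1 names Table 5.1 for LVEF decisions, and no sentence makes the general grade rule override that cell. Consultation is a backstop, because a site that sees the LVEF cell satisfied may see no question to raise.

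The overlap with the discontinuation cell is weaker than the overlap with the withhold cell. The list layout of that cell is hard to recover from the available text, so nothing here rests on its exact logic.

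**Conclusion.** The inconsistency is real and minor. Read on its own, the LVEF resumption cell permits a restart while the same row's withhold criterion is still met, and no text says which rule governs. This can happen only at baselines above 70% (points) or above 62.5% (relative).

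The table of readings shows what is possible, not how likely it is. The documents give no baseline LVEF distribution and no rate of LVEF events, so a reader who takes this as a common event or a demonstrated cardiac hazard goes beyond them. The 6- or 9-week gap assumes a hold at Cycle 3 and no earlier scan, although earlier scans are allowed when clinically indicated. A reader might also look for a consequence for the primary result; none follows for PFS, power or alpha. It is worth considering at the next amendment as a patient-safety consistency point.

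**What to change.** Make three wording changes in the LVEF row at the next protocol amendment.

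1. Resumption cell: *LVEF of at least 50% and no longer more than 20% below baseline on the 3-week repeat scan.* If the team meant a full return to baseline, state that instead; it also removes the conflict. The bracketed alternative can go, since eligible baselines are 50% or more.
2. State once whether 20% means percentage points or a relative change. The choice is clinical.
3. Add that patritumab/placebo is not resumed while any withhold criterion in the row is still met. This settles precedence as well as the numerical overlap.

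The withhold and discontinuation cells, readings of 40–49%, and footnote b can stay as they are, with medical-monitor consultation.

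No new scan or visit is needed, because the 3-week repeat is already required. The downside is that a few subjects with high baseline LVEF may stay off drug, or be discontinued, who might otherwise have restarted.

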**Table 5.2: Dose Delays/Reductions for Toxicities Related to Patritumab**

Grade	Action
1	Continue current dose level
2	Continue current dose level
3	Discontinue patritumab/placebo for up to 3 weeks until the event has recovered to Grade 1 or baseline. a Administer patritumab at a dose that is decreased by one dose level for subsequent cycles. A maximum of 1 dose reduction from the 9 mg/kg IV maintenance dose to 6 mg/kg IV maintenance dose will be permitted. No dose reductions below patritumab 6 mg/kg will be allowed.
4	Discontinue patritumab/placebo for up to 3 weeks until the event recovers to Grade 1 or baseline. a Discuss the event with the sponsor's Medical Monitor or designee before restarting patritumab/placebo. If the investigator and the sponsor's Medical Monitor/designee agree, the weekly maintenance dose will also be decreased from 9 mg/kg IV to 6 mg/kg IV.

a If the subject fails to recover to Grade 1 or baseline and dose must be delayed >3 weeks, the subject will be withdrawn from all study treatment, but should continue to undergo all follow-up evaluations

To receive patritumab, a subject's ANC must be  $\geq 1.5 \times 10^9/L$  ( $\geq 1500/mm^3$ ) and platelet count must be  $\geq 100 \times 10^9/L$  ( $\geq 100,000/mm^3$ ). Patritumab may be withheld for up to 3 weeks to allow cell counts to recover to these values. Dose administration may be delayed no more than 3 weeks to allow for recovery. If the dose is delayed more than 3 weeks, the subject will be withdrawn from study treatment, unless discussed and agreed with the sponsor.

All subjects should be carefully monitored for possible infusion reactions during the administration of patritumab/placebo. If, during infusion, a subject experiences mild to moderate symptoms suggestive of infusion reaction (such as fever and chills, with or without nausea/vomiting, pain, headache, dizziness, dyspnea, hypotension), slow down the infusion up to 120 minutes (see Section 3.1.2.1 for administration of patritumab/placebo). All subsequent infusions should be administered at the same slow rate (up to 120 minutes).

Interrupt patritumab/placebo infusion in all subjects experiencing severe infusion reactions (eg, dyspnea, clinically significant hypotension) and administer interventional medical therapy, which may include: epinephrine, corticosteroids, diphenhydramine, bronchodilators, and oxygen. Subjects should be evaluated and carefully monitored until complete resolution of signs and symptoms.

Subjects experiencing severe infusion reactions will be permanently discontinued.

In the event of a dose reduction, the dose change(s) must be captured in the eCRF. If questions or considerations regarding dose modification arise or a specific dose modification is needed, the medical monitor or designee should be consulted. The contact information for the Daiichi Sankyo medical monitor is located in Section 15.2.1.1.

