### Study Treatment Administration

- Administer patritumab IV (infused once every 3 weeks) as specified in Section 3.1.2
- Administer cetuximab IV (infused weekly) as specified in Section 3.1.2
- Administer cisplatin or carboplatin IV (infused every 3 weeks, for a maximum of 6 cycles) as specified in Section 3.1.2

#### 6.2.7. Cycle 4 and all Subsequent Cycles, Day 1

##### 6.2.7.1. Day 1

- Physical examination\*
- Vital signs\*
- Weight\*
- ECOG Performance Status (Section 10.1)
- At visits for every third subsequent cycle (eg, Cycles 6, 9, 12 ...) conduct an echocardiogram or MUGA scan (the same test must be used for a subject throughout the study)
- Record concomitant medications and AEs\*
- Have subject complete the PRO assessments before any study-related procedures are performed
- Collect blood sample preinfusion for CBC with differential and platelet count\*
- Collect blood sample preinfusion for serum chemistries\*

*Note: \* Can be collected on Days 8 and 15 in Cycle 4 and all subsequent cycles at the discretion of the Investigator.*

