Tumor assessments r		X											X s	X				
Survival follow-up															X t			
Additional biomarker blood samples u				X u							X u		X u		X u			

a Last dose of any study drug administered.

b Informed consent for main study (mandatory) and pharmacogenomics (optional).

c Height measured only at Screening.

d These assessments can be performed within 3 days prior to visit.

e Echocardiograms/MUGA scans will be performed at Screening, Cycle 3, at every third subsequent cycle, and End-of-Study Visit. Additional echocardiograms/MUGA scans and electrocardiograms may be performed at the discretion of the investigator. The same test (echocardiogram or MUGA) must be used for a subject throughout the study.

f Collect SAEs only related to the biopsy procedure.

g At 40 days after the last dose of study drug, a telephone call will be placed to the subject to record adverse events.

h PRO assessments will be administered before any study-related procedures are performed.

i Results must be available prior to dosing.

j At Screening, either GFR or the estimated serum creatinine clearance (mL/min) as an estimate of GFR will be calculated. The estimated serum creatinine clearance rate (CrCl; mL/min) will be calculated using the modified Cockcroft-Gault equation ([Appendix 17.1](#)). The estimated GFR will also be calculated before each cisplatin or carboplatin administration. This will be performed only until completion of chemotherapy.

k Intensive serum PK in a subgroup of 30 subjects samples will be collected. See [Table 8.2](#) for detailed information on sampling times.

l See [Table 8.1](#) for detailed information on sampling times.

m Pregnancy test must be confirmed negative before dosing. Additional pregnancy testing may be done at the discretion of the Investigator and/or if required by local regulations for women of child-bearing potential.

n Patritumab administered initially at 18 mg/kg and thereafter 9 mg/kg every 3 weeks as a continuous intravenous infusion over 60 minutes (±10 minutes). Infusion times can be extended to a maximum of 120 minutes for subjects unable to tolerate the 60-minute infusion.

o Cetuximab infusions administered initially at 400 mg/m^2 IV over 2 hours and 250 mg/m^2 over 1 hour weekly. Cetuximab is administered 60 minutes after patritumab administration. Cetuximab is given on Days 1, 8, and 15.

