**Table 17.3: Schedule of Events for Extension Phase**

	Additional cycles		Every 3 months	End of Treatment	40 days after last dose a
	Predose	Dosing			
Visit Window (Days)					
Physical Exam	X			X	
Vital Signs	X			X	
Adverse Events	X				X
CBC diff and platelets b	X b			X b	
Serum chemistries b	X b			X b	
HAHA and PK sample c			X		
Patritumab Adm d		X			
Cetuximab Adm e		X			
Additional biomarker blood samples			X	X	X

a Last dose of any study drug administered.

b CBC and chemistries must be performed within 3 days of dosing.

c For subjects with positive HAHA at the End of Study Treatment visit, additional serum HAHA samples should be collected every 3 months up to 1 year from the last dose of study drug or if the subject starts another therapy for cancer, or withdraws consent from the study, whichever occurs first.

d Patritumab administered at 9 mg/kg every 3 weeks as a continuous intravenous infusion over 60 minutes ( $\pm 10$  minutes). Infusion times can be extended to a maximum of 120 minutes for subjects unable to tolerate the 60 minute infusion.

e Cetuximab is infused at 250 mg/m^2 over 1 hour weekly. Cetuximab can be administered directly after patritumab administration.

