- h PRO assessments will be administered before any study-related procedures are performed.
- i Results must be available prior to dosing.
- j At Screening, either GFR or the estimated serum creatinine clearance (mL/min) as an estimate of GFR will be calculated. The estimated serum creatinine clearance rate (CrCl; mL/min) will be calculated using the modified Cockcroft-Gault equation (Appendix 17.1). The estimated GFR will also be calculated before each cisplatin or carboplatin administration. This will be performed only until completion of chemotherapy.
- k Intensive serum PK in a subgroup of 30 subjects samples will be collected. See **Error! Reference source not found.** in the protocol for detailed information on sampling times.
- l See **Error! Reference source not found.** in the protocol for detailed information on sampling times.
- m Pregnancy test must be confirmed negative before dosing. Additional pregnancy testing may be done at the discretion of the Investigator and/or if required by local regulations for women of child-bearing potential.
- n Patritumab administered initially at 18 mg/kg and thereafter 9 mg/kg every 3 weeks as a continuous intravenous infusion over 60 minutes (±10 minutes). Infusion times can be extended to a maximum of 120 minutes for subjects unable to tolerate the 60-minute infusion.
- o Cetuximab infusions administered initially at 400 mg/m² IV over 2 hours and 250 mg/m² over 1 hour weekly. Cetuximab is administered 60 minutes after patritumab administration. Cetuximab is given on Days 1, 8, and 15.
- p Cisplatin infusions administered at 100 mg/m² IV over 1 hour and every 3 weeks up to a maximum of 6 cycles. For pre- and post-treatment hydration see **Section Error! Reference source not found.** in the protocol and according to institutional standards. Creatinine clearance required prior to cisplatin administration. Cisplatin administered 1 hour after cetuximab administration. If carboplatin is selected instead of cisplatin, administer carboplatin at AUC of 5 over 30-60 minutes every 3 weeks for a maximum of 6 cycles. See **Section Error! Reference source not found.** in the protocol for carboplatin.

- q Genetic sampling is optional.
- r Tumor measurements will be assessed per RECIST Version 1.1. Baseline scans to be performed as part of eligibility during Screening. Existing radiographic scans can be used for the baseline evaluation if the scans were performed within 4 weeks prior to randomization.

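### Protocol Table 5.2, Grade 4 row, calls the patritumab maintenance dose weekly; the trial gives it every 3 weeks

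*Protocol*

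**What the plan says.** Table 5.2 (Protocol Section 5.1.7.1) gives the action by grade for toxicities related to patritumab. For Grade 4, patritumab/placebo is stopped for up to 3 weeks pending recovery, and the site must consult the sponsor's "Medical Monitor or designee before restarting patritumab/placebo". If both sides agree, "the weekly maintenance dose will also be decreased from 9 mg/kg IV to 6 mg/kg IV".

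The visit procedures for Cycles 2 and 3 read "Administer patritumab IV (infused once every 3 weeks) as specified in Section 3.1.2" and, for the weekly drug, "Administer cetuximab IV (infused weekly) as specified in Section 3.1.2". Both instructions recur for Cycle 4 onward. Footnote n of the main-study Schedule of Events (Table 17.2) reads "Patritumab administered initially at 18 mg/kg and thereafter 9 mg/kg every 3 weeks as a continuous intravenous infusion". The extension-phase schedule (Table 17.3, footnote d) reads "Patritumab administered at 9 mg/kg every 3 weeks as a continuous intravenous infusion over 60 minutes". The SAP's copy of the schedule (Table 3.1.1, footnote n) has "thereafter 9 mg/kg every 3 weeks as a continuous intravenous infusion over 60 minutes".

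Table 5.1, immediately before Table 5.2, covers adverse events of Grade 3 or higher. It gives the same step in dose with no interval attached: "Reduce patritumab maintenance dose from 9 mg/kg to 6 mg/kg".

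**The concern.** The Grade 4 row attaches to patritumab an interval that the trial does not use. Sites consult this row when deciding how to restart an investigational antibody after a life-threatening toxicity, so the dose and interval there should agree with the dosing schedule.

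What is at stake is a possible dosing error after a Grade 4 event. A rule meant to lower exposure could, on one misreading, raise it. Subjects already attend on Days 8 and 15 for cetuximab, so a weekly visit at which an infusion could be given does exist. Nothing statistical depends on the word.

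**Working it through.** The plan states no figure to reproduce here. The check compares every statement of the patritumab interval and then converts each reading of the Grade 4 sentence to dose per 21-day cycle.

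**Step 1. Which drug does the sentence mean?** Table 5.2 is for patritumab and the doses are in mg/kg. Cetuximab is dosed in mg/m² (Protocol Section 3.1.2.1). The word cannot refer to cetuximab.

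**Step 2. What interval is given elsewhere?**

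| Place | Patritumab maintenance interval |
|---|---|
| Protocol synopsis, dosage section | every 3 weeks |
| Protocol 1.1.1.5, recommended phase 2 dose and clinical pharmacology | every 3 weeks |
| Protocol 3.1.2.1, treatment administration | every 3 weeks from cycle 2 |
| Protocol 6.2.6.2 and 6.2.7.1, visit procedures | every 3 weeks |
| Protocol Table 17.2, footnote n | every 3 weeks |
| Protocol Table 17.3, footnote d | every 3 weeks |
| SAP 3.1 text, and footnotes to Tables 3.1.1 and 3.1.2 | every 3 weeks |
| Protocol Table 5.2, Grade 4 row | weekly |

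A cycle is 21 days (Protocol 3.1.5). Protocol 6.2.4 and 6.2.5 list only cetuximab for administration on Days 8 and 15. The exposure formulas in SAP 8.3.6 agree: treatment duration adds 21 days after the last patritumab dose but 7 days after the last cetuximab dose.

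Protocol 1.1.1.4 mentions dosing every 2 weeks, and every 2 to 3 weeks. That is pharmacokinetic background and not this trial's schedule, and it is not weekly either.

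**Step 3. Could weekly be deliberate?** The Grade 3 row of the same table makes the same 9 to 6 mg/kg step, attaches no weekly interval, and ties the reduced dose to later cycles. Table 5.1 also gives the step without an interval. The Grade 4 sentence describes 9 mg/kg weekly as the starting point, a regimen that no subject is on. It lowers the amount and does not tell anyone to change the frequency.

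**Step 4. Dose per 21-day cycle.** Formula: dose per cycle = dose per infusion × infusions per cycle.

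| Reading | Before | After | Result |
|---|---|---|---|
| Intended (every 3 weeks) | 9 × 1 = 9 mg/kg | 6 × 1 = 6 mg/kg | (9 − 6)/9 = 33% cut |
| Weekly applied to both doses | 9 × 3 = 27 mg/kg | 6 × 3 = 18 mg/kg | (27 − 18)/27 = 33% cut |
| Mixed: true schedule before, weekly after restart | 9 × 1 = 9 mg/kg | 6 × 3 = 18 mg/kg | 18/6 = 3 times intended; 18/9 = 2 times previous |

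The second reading is the literal one, but its starting point does not exist in this trial. Only the third, mixed reading turns a reduction into an increase.

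**The case against.** The strongest reply is that this is an editorial slip that any reader would correct. The operative content of the row, the 6 mg/kg level, is right. The surrounding text resolves the interval several ways:

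- The Grade 3 row refers to later cycles, and a cycle is 21 days.
- The text of Section 5.1.7.1 has patritumab resume after a Grade 3 event at the next scheduled patritumab dose.
- No visit procedure exists for giving patritumab on Days 8 or 15.
- The Medical Monitor must be consulted before a Grade 4 restart.
- Vials can be allocated only through the IxRS (Protocol 5.1.4).

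On this view the threefold and twofold figures require a site to treat an adjective as a new schedule against every dosing instruction.

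Most of that stands as an argument about weight. Misdosing is unlikely, and the multiples belong to a hypothetical worst case. It does not make the word right, and no other text corrects it. The safeguards also have limits: Section 5.1.4 does not say that the IxRS enforces a 21-day interval, and the Medical Monitor would be reading the same table.

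Two further qualifications are fair. Table 5.1 matches the Grade 4 row in dose levels but not in every condition, since only the Grade 4 row makes the reduction depend on agreement with the Medical Monitor. Separately, the text of Section 5.1.7.1 has patritumab resume after a Grade 3 event at the 9 mg/kg maintenance dose, while Tables 5.1 and 5.2 reduce it to 6 mg/kg. That is a different issue, and correcting this word does not settle it.

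**Conclusion.** The point holds. The Grade 4 row of Table 5.2 states a dosing interval that contradicts this trial's schedule throughout the protocol and SAP. Confidence in the textual finding is high.

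Its importance is low: an optional correction. The likely practical effect is nil, because the intended 33% reduction is clear from context and the restart controls apply. The outer bound of 18 mg/kg per cycle instead of 6 assumes that a subject on the every-3-week schedule is restarted weekly despite those controls. Sample size, alpha, power, the endpoint and the analyses are untouched.

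**What to change.** In the Grade 4 row of Protocol Table 5.2, delete *weekly* before *maintenance dose*, or replace it with *every-3-week*. The reduced dose is then 6 mg/kg once per 21-day cycle, consistent with the Grade 3 row, Table 5.1 and the dosing schedule.

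The cost is a one-word protocol clarification. The design, data collection and SAP do not change.
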